8.3 ADVERSE EVENTS AND SERIOUS ADVERSE EVENTS

8.3.1 DEFINITION OF ADVERSE EVENTS

This protocol uses the definition of adverse event from DHHS Office for Human Research Protections (OHRP): Any untoward or unfavorable medical occurrence in a human subject, including any abnormal sign (for example, abnormal physical exam or laboratory finding), symptom, or disease, temporally associated with the subject’s participation in the research, whether or not considered related to the subject’s participation in the research (modified from the definition of adverse events in the 1996 International Conference on Harmonization E-6 Guidelines for Good Clinical Practice).

8.3.2 DEFINITION OF SERIOUS ADVERSE EVENTS

This protocol uses the definition of serious adverse event from DHHS OHRP: any adverse event that results in death; is life-threatening (places the subject at immediate risk of death from the event as it occurred); results in inpatient hospitalization or prolongation of existing hospitalization; results in a persistent or significant disability/incapacity; results in a congenital anomaly/birth defect; or based upon appropriate medical judgment, may jeopardize the subject's health and may require medical or surgical intervention to prevent one of the other outcomes listed in this definition (examples of such events include allergic bronchospasm requiring intensive treatment in the emergency room or at home, blood dyscrasias or convulsions that do not result in inpatient hospitalization, or the development of drug dependency or drug abuse).

8.3.3 CLASSIFICATION OF AN ADVERSE EVENT

8.3.3.1 SEVERITY OF EVENT

All AEs will be assessed by the PI or co-investigators, if the PI is not available. The following guidelines will be used to describe severity:

- **Mild** – Events require minimal or no treatment and do not interfere with the participant's daily activities.
- **Moderate** – Events result in a low level of inconvenience or concern with the therapeutic measures. Moderate events may cause some interference with functioning.
- **Severe** – Events interrupt a participant's usual daily activity and may require systemic drug therapy or other treatment. Severe events are usually potentially life-threatening or incapacitating. Of note, the term "severe" does not necessarily equate to "serious".]

8.3.3.2 RELATIONSHIP TO STUDY INTERVENTION/EXPERIMENTAL MANIPULATION

All AEs will have their relationship to study procedures, including the intervention, assessed by the PI or co-investigators based on temporal relationship and his/her clinical judgment. The degree of certainty about causality will be graded using the categories below.

- **Related** – The AE is known to occur with the study procedures, there is a reasonable possibility that the study procedures caused the AE, or there is a temporal relationship between the study procedures and the event. Reasonable possibility means that there is evidence to suggest a causal relationship between the study procedures and the AE.
- **Not Related** – There is not a reasonable possibility that the study procedures caused the event, there is no temporal relationship between the study procedures and event onset, or an alternate etiology has been established.

8.3.3.3 EXPECTEDNESS

The PI or [name] or [name] (co-investigators on the study) will be responsible for determining whether an AE is expected or unexpected. An AE will be considered unexpected if the nature, severity, or frequency of the event is not consistent with the risk information previously described for the study procedures.

8.3.4 TIME PERIOD AND FREQUENCY FOR EVENT ASSESSMENT AND FOLLOW-UP

The occurrence of an AE or serious adverse event (SAE) may come to the attention of study team members during study visits. All AEs, not otherwise precluded per the protocol, will be captured on the Adverse Event Form. Information to be collected includes event description, time of onset, PI or co-investigator's assessment of severity, relationship to study procedures (assessed only by those with the training and authority to make a diagnosis), and time of resolution/stabilization of the event. All AEs occurring while on study will be documented appropriately regardless of relationship. All AEs will be followed to adequate resolution.

Any medical or psychiatric condition that is present at the time that the participant is screened will be considered as baseline and not reported as an AE. However, if the study participant's condition deteriorates at any time during the study, it will be recorded as an AE.

Changes in the severity of an AE will be documented to allow an assessment of the duration of the event at each level of severity to be performed. Documentation of onset and duration of each episode will be maintained for AEs characterized as intermittent.

The Project Coordinator will record events with start dates occurring any time after informed consent is obtained until 7 (for non-serious AEs) or 30 days (for SAEs) after the last day of study participation. Participants are identified in the EMR as a study participant and for each AE/SAE occurrence, research team members will receive an alert through EMR. AEs or SAEs may also be reported to PA Coach during the course of intervention visits. Events will be followed for outcome information until resolution or stabilization.

8.3.5 ADVERSE EVENT REPORTING

Once [name] (or a co-investigator) is contacted about the adverse event, she / he will make a determination about the reporting requirements in accordance with UNC IRB guidelines.

The PI will report all adverse events to the Safety Officer (SO) on a biannual basis, or as requested. Additionally, the PI or a co-investigator will report any AEs that suggest new or increased risk to participants or others within 7 calendar days of when the PI became aware of the information. For AEs that are not related to participation in the research and do not suggest new or increased risks to the participant, these will be reported at continuing review.

8.3.6 SERIOUS ADVERSE EVENT REPORTING

Once [name] (or a co-investigator) is contacted about a serious adverse event, she / he will make a determination about the reporting requirements in accordance with UNC IRB guidelines. This will include notification of the UNC IRB, as well as the SO, within 24-hours if a study-related death and within 48 hours if another SAE.

8.3.7 REPORTING EVENTS TO PARTICIPANTS

N/A

8.3.8 EVENTS OF SPECIAL INTEREST

N/A

8.3.9 REPORTING OF PREGNANCY

N/A

8.4. UNANTICIPATED PROBLEMS

8.4.1 DEFINITION OF UNANTICIPATED PROBLEMS

This protocol uses the definition of Unanticipated Problems as defined by the Office for Human Research Protections (OHRP). OHRP considers unanticipated problems involving risks to participants or others to include, in general, any incident, experience, or outcome that meets all of the following criteria:

- (1) Unexpected (in terms of nature, severity, or frequency) given (a) the research procedures that are described in the IRB-approved research protocol and informed consent document; and (b) the characteristics of the participant population being studied;
- (2) Related or possibly related to participation in the research. *Possibly related* means there is a reasonable possibility that the incident, experience, or outcome may have been caused by the procedures involved in the research); and
- (3) Suggests that the research places participants or others at a greater risk of harm (including physical, psychological, economic, or social harm) than was previously known or recognized.

OHRP recognizes that it may be difficult to determine whether a particular incident, experience, or outcome is unexpected and whether it is related or possibly related to participation in the research. OHRP notes that an incident, experience, or outcome that meets the three criteria above generally will warrant consideration of substantive changes in the research protocol or informed consent process/document or other corrective actions in order to protect the safety, welfare, or rights of participants or others.

The following corrective actions or substantive changes that could be considered in response to an unanticipated problem include:

- Changes to the research protocol initiated by the investigator prior to obtaining IRB approval to eliminate apparent immediate hazards to subjects;
- modification of inclusion or exclusion criteria to mitigate the newly identified risks;
- implementation of additional procedures for monitoring subjects; suspension of enrollment of new subjects;
- suspension of research procedures in currently enrolled subjects;
- modification of informed consent documents to include a description of newly recognized risks;
- provision of additional information about newly recognized risks to previously enrolled subjects.

Only a small subset of adverse events occurring in human subjects participating in research will meet these three criteria for an unanticipated problem. Furthermore, there are other types of incidents, experiences, and outcomes that occur during the conduct of human subjects research that represent unanticipated problems but are not considered adverse events. For example, some unanticipated problems involve social or economic harm instead of the physical or psychological harm associated with adverse events. In other cases, unanticipated problems place subjects or others at increased risk of harm, but no harm occurs.

8.4.2 UNANTICIPATED PROBLEMS REPORTING

All UPs will be reported to the NIA and the SO within 48 hours of the PI becoming aware of the event.

8.4.3 REPORTING UNANTICIPATED PROBLEMS TO PARTICIPANTS

Participants will be given any new information gained during the course of the study that might affect their willingness to continue participation in the study.

9 STATISTICAL CONSIDERATIONS

9.1 STATISTICAL HYPOTHESES

The aim of this study is to conduct a randomized pilot trial of the refined OA-PCP among n=240 patients with knee and / or hip OA. Sub-aims and hypotheses are:

1. Obtain data on the efficacy of the OA-PCP.

H₁ Participants in OA-PCP intervention will have greater improvement in objectively assessed PA, measured at 6 and 12 months, compared to participants in an attention control group.

H₂ Participants in OA-PCP intervention will have greater improvement in self-reported physical function and pain, measured at 6 and 12 months, compared to participants in an attention control group.

2. Refine the OA-PCP based on feedback from patients, clinic personnel, and community representatives, in preparation for a larger, implementation-focused trial.

9.2 SAMPLE SIZE DETERMINATION

We note that this study is an extended exploratory phase, in which we are interested in obtaining estimates of efficacy that will inform a larger trial that is adequately powered to detect clinically meaningful differences in MVPA. Our sample size was selected on the basis of feasibility for this exploratory study and involvement of a sufficient number participants to adequately assess intervention and study procedures. We provide here a description of expected statistical power for this sample size. Based on previous research on PA

interventions for OA^{98,99}, we expect an effect

size of 0.3-0.7, though have examined a range of possible values from 0.2-0.8 (Table 2). We also account for 10% attrition, based on our prior work. A sample size of 240 participants (120 per group) will provide approximately 80% power at 5% level of significance to detect a small-to-medium effect size of 0.38 or greater for the difference in minutes of MVPA between intervention and control groups, accounting for expected attrition.

$\alpha=0.05$	Power=80%	Power=85%	Power=90%	Power=95%
Effect size	Sample size	Sample size	Sample size	Sample size
0.20	787	900	1053	1301
0.30	351	401	469	579
0.40	198	226	265	327
0.50	128	146	170	210
0.60	90	102	120	148
0.70	68	76	88	110
0.80	52	60	68	84

9.3 POPULATIONS FOR ANALYSES

The primary analyses will be conducted using an intent-to-treat approach. Supportive exploratory analyses may be conducted to consider samples with greater completion of study intervention visits. Since this is an exploratory trial, the nature of these supportive analyses will be based on observed patterns of intervention contacts.

9.4 STATISTICAL ANALYSES PLAN

Preliminary analyses will include generating descriptive statistics for demographic variables, as well as baseline characteristics and follow-up measures. This includes means and standard deviations for continuous variables, and frequencies and percentages for categorical variables. Ranges will also be examined for outliers and to ensure data integrity. Demographics and baseline characteristics will also be described separately by randomized group.

We hypothesize that participants receiving the OA-PCP will have greater improvement in MVPA compared with the attention control group at 6 and 12 months. To determine the effects of the intervention on MVPA, repeated measures will be analyzed using linear mixed effects models, with clinic included as a random effect, to estimate mean change and 95% confidence intervals in MVPA from baseline to 6-month and 12-month time points. This model will account for intra-person clustering for the repeated measures, including a group x time effect. We will use the same modeling strategy for continuous secondary and exploratory outcomes. An advantage of this modeling approach is that it uses all available data; participants are not dropped if they miss a time point. This approach will reduce the overall amount of missing data and could eliminate the need for imputation of missing repeated outcomes¹⁰⁰. However, if we find that missing data are related to measured patient factors (i.e., missing not at random [MNAR]), we will carry out sensitivity analyses by imputing missing values under the MNAR scenario and examining the results. The SAS procedure PROC MI has several options for using multiple imputation in sensitivity analyses based on pattern-mixture models for MNAR data, which model the distribution of a response as the mixture of a distribution of the observed responses and a distribution of the missing responses¹⁰¹. Multiple imputation has the advantage of providing a framework for incorporating information from these variables, while preserving a parsimonious main treatment effect model^{102, 103}. Analyses will be conducted on an intent-to-treat basis and carried out using SAS 9.4 (SAS Institute Inc., Cary, NC). Tests will be two-sided and considered significant at the 0.05 level.

Exploration of Mediators. We are interested in understanding the degree to which various facets of the OA-PCP contribute to improvements in PA and other outcomes. Because the mediating variables of interest (described above) pertain only to the OA-PCP group, our strategy will differ from a traditional mediation analysis approach in the context of a clinical trial. Specifically, we will use linear regression models to assess associations between potential mediating variables and outcomes among individuals in the OA-PCP group. Each potential mediator will be assessed individually, then we will fit a multivariable model including all variables with bivariate associations of $p \leq 0.1$. Analyses will be performed for both 6 and 12 month outcomes.

Exploration of Moderators. We will explore potential differential treatment effects based on participant characteristics, particularly gender, age and baseline PAVS score. The latter is of interest to help inform the inclusion criterion for a larger trial; if individuals with higher baseline PA (though not meeting DHHS recommendations) make little additional improvement in PA, we may focus on individuals with lower PA levels at screening. For assessment of differential treatment effects, we will conduct stratified analyses based on participant characteristics (e.g., men / women, age categories by decade, quartiles of baseline PAVS scores). We propose this strategy because the study is not powered to detect interactions between treatment group and participant characteristics. We will also use multivariable logistic regression^{104,105} and recursive partitioning (RP)^{106,107} to explore multidimensional subgroups that exhibit heterogeneous treatment effects; these analyses will focus on our a priori characteristics of interest but also explore additional variables.

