4.4 END-OF-STUDY DEFINITION

[figure not shown]

Figure 2: Study Design

A participant is considered to have completed the study if he or she has completed 12-month follow-up assessment.

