10.1.2 STUDY DISCONTINUATION AND CLOSURE

This study may be temporarily suspended or prematurely terminated if there is sufficient reasonable cause. Written notification, documenting the reason for study suspension or termination, will be provided by the suspending or terminating party to study participants, investigator, funding agency, and regulatory authorities. If the study is prematurely terminated or suspended, the PI will promptly inform study participants, the IRB, and sponsor/funding agency and will provide the reason(s) for the termination or suspension. Study participants will be contacted, as applicable, and be informed of changes to study visit schedule.

Circumstances that may warrant termination or suspension include, but are not limited to:

- Determination of unexpected, significant, or unacceptable risk to participants

- Demonstration of efficacy that would warrant stopping
- Insufficient compliance to protocol requirements
- Data that are not sufficiently complete and/or evaluable
- Determination that the primary endpoint has been met
- Determination of futility

The study may resume once concerns about safety, protocol compliance, and data quality are addressed, and satisfy the funding agency, sponsor, IRB or other relevant regulatory or oversight bodies (OHRP, SO).

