10.1.4 FUTURE USE OF STORED DATA

Data collected for this study will be analyzed and stored on a secure UNC server. After the study is completed, the de-identified data will be made available to other researchers, available by request to the PI. Investigators requesting study data must adhere to regulatory requirements for data use (e.g., IRB approvals, data use agreements). No biological samples are collected for this study.

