10.1.11 PUBLICATION AND DATA SHARING POLICY

This study will be conducted in accordance with the following publication and data sharing policies and regulations:

- National Institutes of Health (NIH) Public Access Policy, which ensures that the public has access to the published results of NIH funded research. It requires scientists to submit final peer-reviewed journal manuscripts that arise from NIH funds to the digital archive PubMed Central upon acceptance for publication.

This study will comply with the NIH Data Sharing Policy and Policy on the Dissemination of NIH-Funded Clinical Trial Information and the Clinical Trials Registration and Results Information Submission rule. As such, this trial will be registered at ClinicalTrials.gov, and results information from this trial will be submitted to ClinicalTrials.gov. In addition, every attempt will be made to publish results in peer-reviewed journals. Data from this study may be requested from other researchers after the completion of the primary endpoint by contacting the study PI. Considerations for ensuring confidentiality of these shared data are described in Section 10.1.3.

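### Does the plan need to name which time point, 6 or 12 months, decides the primary MVPA hypothesis?

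*Combined protocol and SAP*

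**What the plan says.** Section 9.4 states the hypothesis for both follow-up visits: "We hypothesize that participants receiving the OA-PCP will have greater improvement in MVPA compared with the attention control group at 6 and 12 months". The synopsis and Sections 3, 4.1 and 9.1 also state H1 for 6 and 12 months together. The analysis is a linear mixed model that estimates change in MVPA from baseline to each visit with 95% confidence intervals. On its structure, 9.4 says: "This model will account for intra-person clustering for the repeated measures, including a group x time effect". Tests are two-sided at 0.05.

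Section 9.2 says: "A sample size of 240 participants (120 per group) will provide approximately 80% power at 5% level of significance". The effect size is 0.38, and the comparison is described as being "for the difference in minutes of MVPA between intervention and control groups", with no visit attached. The same section calls the study exploratory and says that the sample size was chosen for feasibility.

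Sections 3 and 4.1 tie 12 months to the end of the coaching calls and give 6 months the role of showing the time course. Neither visit is called primary.

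Three administrative sections bear on the timing. Section 10.1.2 lists "Determination that the primary endpoint has been met" among circumstances that may warrant closing the study. Section 10.1.11 says: "Data from this study may be requested from other researchers after the completion of the primary endpoint". Section 10.1.4 says: "After the study is completed, the de-identified data will be made available to other researchers".

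**The concern.** A hypothesis covering two visits, a 5% significance level and no named deciding contrast leave room to choose after the results are known. If the 6-month difference is significant and the 12-month difference is not, the plan does not say whether H1 is supported. Such a split is quite possible even when the intervention works equally well at both visits.

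The administrative text seems to make this worse. Section 10.1.2 speaks of the primary endpoint being met, and 10.1.11 of its being complete, as if each were a single event. If the endpoint counted as complete at 6 months, 10.1.11 would open data requests about six months before the last 12-month assessments, whereas 10.1.4 waits for the end of the study. At stake would be the false-positive rate, the meaning of the 80% power figure, and the date of data release.

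**Working it through.** **Inputs from the documents.** 240 randomised 1:1, so 120 per group (9.2, 4.1); 10% attrition (9.2), so 120 × 0.9 = 108 evaluable per group; standardised effect d = 0.38 (9.2); two-sided 0.05 (9.4).

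**Assumptions not in the documents.** The correlation r between the 6- and 12-month test statistics is taken from 0.3 to 0.9. The effect is taken as 0.38 at both visits.

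**Step 1: the plan's own figure.** The noncentrality is d × √(n/2) = 0.38 × √54 = 2.792. A two-sample t test with 214 degrees of freedom gives power 79.4%. The normal approximation gives Φ(2.792 − 1.960) = Φ(0.832) = 79.7%. Both agree with the stated 80% or so. Nothing in this calculation depends on which visit is meant, so the figure is right for either and lacks only a label.

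**Step 2: what each reading would imply.** The two statistics are treated as bivariate normal with unit variances, correlation r, and mean 0 (null) or 2.792 (alternative) at both visits.

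- Either visit: error = 1 − P(|Z₁| < 1.96 and |Z₂| < 1.96) under the null.
- Both visits: power = P(Z₁ > 1.96 and Z₂ > 1.96) under the alternative.
- Exactly one visit significant: 2 × (0.797 − power for both).
- Joint group-by-time test on 2 degrees of freedom: noncentrality λ = 2 × 2.792² / (1 + r) = 15.595 / (1 + r), compared with the chi-square critical value 5.991; error 5% by construction.

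| r | Either visit: two-sided error | Both visits: power | Exactly one significant | Joint test: λ | Joint test: power |
|---|---|---|---|---|---|
| 0.3 | 9.5% | 66.2% | 27.0% | 12.00 | 88.3% |
| 0.5 | 9.1% | 68.4% | 22.8% | 10.40 | 83.1% |
| 0.7 | 8.3% | 71.0% | 17.6% | 9.17 | 77.9% |
| 0.9 | 7.0% | 74.7% | 10.1% | 8.21 | 72.9% |

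Counting only results that favour OA-PCP, the either-visit error is 4.8% to 3.5%, against 2.5% for one contrast.

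So inflation above 5% arises only if analysts let either visit suffice without adjustment, a rule the plan does not state. A single contrast and the joint test of the term that 9.4 names both hold 5%. Requiring both visits is conservative and costs power only.

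**Step 3: the administrative sections side by side.**

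- *10.1.11 and 10.1.4.* The first concerns when data may be requested, the second when they are made available. The two acts can have different dates. Section 3 defines the endpoint as assessed at baseline, 6 and 12 months, so its natural completion is the 12-month visit. The six-month gap needs a 6-month-only reading, which no section supports. Even an either-visit rule needs the 12-month data before the endpoint is complete.
- *4.4.* "A participant is considered to have completed the study if he or she has completed 12-month follow-up assessment". This defines completion for a participant, not for the study, and it too points to 12 months.
- *10.1.2.* This is a general list of circumstances that may warrant stopping. Section 9 plans no interim efficacy analysis, so naming a contrast would not make the item operational.
- *9.2.* It describes power for a difference in MVPA. It neither uses the term primary endpoint nor describes an event.

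**The case for a change.** The strongest argument for a change is the split result. With a true effect of 0.38 at both visits, 27% to 10% of trials would be significant at exactly one, and the plan does not say what to conclude. The trial is exploratory, but it still states a directional hypothesis, a 5% level and a power figure, and its estimates are meant to inform a larger trial. One sentence would settle the matter with no change in sample size.

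Part of this stands. The deciding contrast is not named, and Sections 3 and 4.1 lean towards 12 months without designating it. The cost is somewhat more than one sentence, though, because H1 names both visits in the synopsis and in Sections 3, 4.1, 9.1 and 9.4, and all would need to be aligned. Nor is the choice forced. The wording of H1 supports a both-visits prediction at least as well as 12 months alone, and the model term in 9.4 supports a joint test. Reasonable statisticians would differ. A split result would in any case be visible, since both estimates and their intervals are to be reported.

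**Conclusion.** The plan leaves the deciding contrast for H1 unnamed, and no change follows. This is missing detail in an exploratory trial sized on feasibility, whose purpose is to estimate efficacy for a larger trial. Followed as written, it yields between-group estimates with 95% confidence intervals at both visits, from which readers can judge the size and time course of the effect. The 80% power figure is correct for one single-time contrast (79.4%). The either-visit error of 9.5% to 7.0% and the both-visits power of 66% to 75% describe rules that the plan does not adopt. They rest on an assumed correlation of 0.3 to 0.9, and the power figures also on an equal effect at both visits. The joint test holds 5% with power of 88% to 73% on the same assumptions. The supposed conflicts with 9.2, 10.1.2, 10.1.4 and 10.1.11 do not hold. Authors who wish to label the contrast could do so. Twelve months, with 6 months supportive, fits Sections 3 and 4.1 best, and a joint group-by-time test is a fair alternative.
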